8.2 Assessing and Recording Adverse Events

An adverse event is defined as any untoward medical occurrence in a patient or clinical investigation subject administered a pharmaceutical product and which does not necessarily have to have a causal relationship with this treatment. An adverse event can therefore be any unfavorable and unintended sign (including an abnormal laboratory finding, for example), symptom, or disease temporally associated with the use of a medicinal product or protocol-specified procedure, whether or not considered related to the medicinal product or protocol-specified procedure. Any worsening (i.e., any clinically significant adverse change in frequency and/or intensity) of a preexisting condition that is temporally associated with the use of the Merck's product, is also an adverse event.

Changes resulting from normal growth and development that do not vary significantly in frequency or severity from expected levels are not to be considered adverse events. Examples of this may include, but are not limited to, teething, typical crying in infants and children and onset of menses or menopause occurring at a physiologically appropriate time.

Merck product includes any pharmaceutical product, biological product, device, diagnostic agent or protocol-specified procedure, whether investigational (including placebo or active comparator medication) or marketed, manufactured by, licensed by, provided by or distributed by Merck for human use.

Adverse events may occur during the course of the use of Merck product in clinical trials or within the follow-up period specified by the protocol, or prescribed in clinical practice, from overdose (whether accidental or intentional), from abuse and from withdrawal.

Adverse events may also occur in screened subjects during any pre-allocation baseline period as a result of a protocol-specified intervention, including washout or discontinuation of usual therapy, diet, placebo treatment or a procedure.

Progression of the cancer under study is not considered an adverse event unless it is considered to be drug related by the investigator.

All adverse events will be recorded from first day of study drug administration through 30 days following cessation of treatment and at each examination on the Adverse Event case report forms/worksheets. The reporting timeframe for adverse events meeting any serious criteria is described in section 7.2.3.1.

8.2.1 Definition of an Overdose for This Protocol and Reporting of Overdose to the Sponsor and to Merck

For purposes of this trial, an overdose of pembrolizumab will be defined as any dose of 1,000 mg or greater (\geq 5 times the indicated dose). No specific information is available on the treatment of overdose of pembrolizumab. Appropriate supportive treatment should be provided if clinically indicated. In the event of overdose, the subject should be observed closely for signs of toxicity. Appropriate supportive treatment should be provided if clinically indicated.

If an adverse event(s) is associated with ("results from") the overdose of a Merck product, the adverse event(s) is reported as a serious adverse event, even if no other seriousness criteria are met.

If a dose of Merck's product meeting the protocol definition of overdose is taken without any associated clinical symptoms or abnormal laboratory results, the overdose is reported as a non-serious Event of Clinical Interest (ECI), using the terminology "accidental or intentional overdose without adverse effect."

All reports of overdose with and without an adverse event must be reported within 24 hours to the UC CCC Cancer Clinical Trials Office and Principal Investigator and within 2 working days hours to Merck Global Safety. (Attn: Worldwide Product Safety; [contact])

8.2.2 Reporting of Pregnancy and Lactation to the Sponsor and to Merck

Although pregnancy and lactation are not considered adverse events, it is the responsibility of investigators or their designees to report any pregnancy or lactation in a subject (spontaneously reported to them), including the pregnancy of a male subject's female partner that occurs during the trial or within 120 days of completing the trial completing the trial, or 30 days following cessation of treatment if the subject initiates new anticancer therapy, whichever is earlier. All subjects and female partners of male subjects who become pregnant must be followed to the completion/termination of the pregnancy. Pregnancy outcomes of spontaneous abortion, missed abortion, benign hydatidiform mole, blighted ovum, fetal death, intrauterine death, miscarriage and stillbirth must be reported as serious events (Important Medical Events). If the pregnancy continues to term, the outcome (health of infant) must also be reported.

Such events must be reported within 24 hours to the UC CCC Cancer Clinical Trials Office and Principal Investigator and within 2 working days to Merck Global Safety. (Attn: Worldwide Product Safety; [contact])

8.2.3 Immediate Reporting of Adverse Events to the Sponsor and to Merck

8.2.3.1 Serious Adverse Events

A serious adverse event is any adverse event occurring at any dose or during any use of Merck's product that:

- Results in death;
- Is life threatening;
- Results in persistent or significant disability/incapacity;
- Results in or prolongs an existing inpatient hospitalization;
- Is a congenital anomaly/birth defect;
- Is a new cancer (that is not a condition of the study);
- Is associated with an overdose;
- Is an other important medical event

Refer to Table 6 for additional details regarding each of the above criteria.

Any serious adverse event, or follow up to a serious adverse event, including death due to any cause other than progression of the cancer under study that occurs to any subject from first day of study drug administration through 90 days following cessation of treatment, or the initiation of new anti-cancer therapy, whichever is earlier, whether or not related to Merck product, must be reported within 24 hours to the UC CCC Cancer Clinical Trials Office and Principal Investigator and within 2 working days to Merck Global Safety.

Non-serious Events of Clinical Interest will be forwarded to Merck Global Safety and will be handled in the same manner as SAEs.

Additionally, any serious adverse event, considered by an investigator who is a qualified physician to be related to Merck product that is brought to the attention of the investigator at any time outside of the time period specified in the previous paragraph also must be reported immediately to the UC CCC Cancer Clinical Trials Office and Principal Investigator and to Merck.

SAE reports and any other relevant safety information are to be forwarded to the Merck Global Safety [contact]

A copy of all 15 Day Reports and Annual Progress Reports is submitted as required by FDA, European Union (EU), Pharmaceutical and Medical Devices agency (PMDA) or other local regulators. Investigators will cross reference this submission according to local regulations to the Merck Investigational Compound Number (IND, CSA, etc.) at the time of submission. Additionally investigators will submit a copy of these reports to Merck & Co., Inc. (Attn: Worldwide Product Safety; [contact]) at the time of submission to FDA.

All subjects with serious adverse events must be followed up for outcome.

8.2.3.2 Unexpected Events

Unexpected events are those not listed at the observed specificity or severity in the protocol, informed consent, investigator brochure, or FDA-approved package insert. An event is considered unexpected if it is listed as occurring within the class of drugs or otherwise expected from the drug's pharmacological properties but which has not been previously observed with this specific investigational agent.

8.2.3.3 Adverse Reactions

An adverse event is considered to be an adverse reaction if there evidence to suggest a causal relationship to the study agent. This may include a single occurrence of an event strongly associated with drug exposure (e.g. Stevens-Johnson Syndrome), one or more occurrence of an event otherwise uncommon is the study population, or an aggregate analysis of specific events occurring at greater than expected frequency.

8.2.3.4 Events of Clinical Interest

Selected non-serious and serious adverse events are also known as Events of Clinical Interest (ECI) and must be recorded as such on the Adverse Event case report forms/worksheets and reported within 24 hours to the UC CCC Cancer Clinical Trials Office and Principal Investigator and within 2 working days to Merck Global Safety. (Attn: Worldwide Product Safety; [contact])Events of clinical interest for this trial include:

- 1. an overdose of Merck product, as defined in Section 7.2.1 Definition of an Overdose for This Protocol and Reporting of Overdose to the Sponsor, that is not associated with clinical symptoms or abnormal laboratory results.
- 2. an elevated AST or ALT lab value that is greater than or equal to 3X the upper limit of normal and an elevated total bilirubin lab value that is greater than or equal to 2X the upper limit of normal and, at the same time, an alkaline phosphatase lab value that is less than 2X the upper limit of normal, as determined by way of protocol-specified laboratory testing or unscheduled laboratory testing.*

*Note: These criteria are based upon available regulatory guidance documents. The purpose of the criteria is to specify a threshold of abnormal hepatic tests that may require an additional evaluation for an underlying etiology.

Subjects should be assessed for possible ECIs prior to each dose. Lab results should be evaluated and subjects should be asked for signs and symptoms suggestive of an immune-related event. Subjects who develop an ECI thought to be immune-related should have additional testing to rule out other etiologic causes. If lab results or symptoms indicate a possible immune-related ECI, then additional testing should be performed to rule out other etiologic causes. If no other cause is found, then it is assumed to be immune-related.

	associated with an adverse event is considered a non-serious event of clinical interest and must be reported within 24 hours.					
	Other important medical events that may not result in death, not be life threatening, or not require hospitalization may be considered a serious adverse event when,					
		priate medical judgment, the event may jeopardize the subject and may require medical or surgical intervention to prevent one of the outcomes				
	listed previously (designated above by a †).					
Duration		d stop dates of the adverse event. If less than 1 day, indicate the appropriate length of time and units				
Action taken	Did the adverse event cause the Merck product to be discontinued?					
Relationship to	Did the Merck product cause the adverse event? The determination of the likelihood that the Merck product caused the adverse event will be provided by an					
test drug	investigator who is a qualified physician. The investigator's signed/dated initials on the source document or worksheet that supports the causality noted on the					
	form, ensures that a medically qualified assessment of causality was done. This initialed document must be retained for the required regulatory time frame. The criteria below are intended as reference guidelines to assist the investigator in assessing the likelihood of a relationship between the test drug and the adverse even					
	1	ailable information.				
	The following components are to be used to assess the relationship between the Merck product and the AE; the greater the correlation with the components and their respective elements (in number and/or intensity), the more likely the Merck product caused the adverse event (AE):					
	Exposure	Is there evidence that the subject was actually exposed to the Merck product such as: reliable history, acceptable compliance assessment (pill count, diary, etc.), expected pharmacologic effect, or measurement of drug/metabolite in bodily specimen?				
	Time Course	Did the AE follow in a reasonable temporal sequence from administration of the Merck product?				
		Is the time of onset of the AE compatible with a drug-induced effect (applies to trials with investigational medicinal product)?				
	Likely Cause	Is the AE not reasonably explained by another etiology such as underlying disease, other drug(s)/vaccine(s), or other host or environmental factors				

Relationship	The following com	The following components are to be used to assess the relationship between the test drug and the AE: (continued)		
to Merck	Dechallenge	Was the Merck product discontinued or dose/exposure/frequency reduced?		
product		If yes, did the AE resolve or improve?		
(continued)		If yes, this is a positive dechallenge. If no, this is a negative dechallenge.		
		(Note: This criterion is not applicable if: (1) the AE resulted in death or permanent disability; (2) the AE resolved/improved despite continuation		
		of the Merck product; or (3) the trial is a single-dose drug trial); or (4) Merck product(s) is/are only used one time.)		
Rechallenge Was the subject re-exposed to the Merck product in this study?				
		If yes, did the AE recur or worsen?		
		If yes, this is a positive rechallenge. If no, this is a negative rechallenge.		
		(Note: This criterion is not applicable if: (1) the initial AE resulted in death or permanent disability, or (2) the trial is a single-dose drug trial); or		
		(3) Merck product(s) is/are used only one time).		
		NOTE: IF A RECHALLENGE IS PLANNED FOR AN ADVERSE EVENT WHICH WAS SERIOUS AND WHICH MAY HAVE BEEN		
		CAUSED BY THE MERCK PRODUCT, OR IF REEXPOSURE TO THE MERCK PRODUCT POSES ADDITIONAL POTENTIAL		
		SIGNIFICANT RISK TO THE SUBJECT, THEN THE RECHALLENGE MUST BE APPROVED IN ADVANCE BY THE STUDY PI AS		
		PER DOSE MODIFICATION GUIDELINES IN THE PROTOCOL.		
	Consistency	Is the clinical/pathological presentation of the AE consistent with previous knowledge regarding the Merck product or drug class pharmacology		
	with Trial	or toxicology?		
	Treatment			
	Profile			
The assessment of relationship will be reported on the case report forms /worksheets by an investigator who is a qualified physician according to his/her best clinical judgment, including consideration of the above elements.				
Record one of the following		Use the following scale of criteria as guidance (not all criteria must be present to be indicative of a Merck product relationship).		
Yes, there is a reasonable possibility of Merck product relationship.		There is evidence of exposure to the Merck product. The temporal sequence of the AE onset relative to the administration of the Merck product is reasonable. The AE is more likely explained by the Merck product than by another cause.		
No, there is not a reasonable possibility Merck product relationship		Subject did not receive the Merck product OR temporal sequence of the AE onset relative to administration of the Merck product is not reasonable OR there is another obvious cause of the AE. (Also entered for a subject with overdose without an associated AE.)		

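### Table 6 words its causality and action-taken items for the Merck product (pembrolizumab) only, although the protocol elsewhere asks about both drugs and the safety objective concerns the combination

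*Combined protocol and SAP*

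**What the plan says.** Table 6 (Section 8.2.4) sets out how the investigator evaluates each adverse event.

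- Action taken: "Did the adverse event cause the Merck product to be discontinued".
- Causality: "Did the Merck product cause the adverse event". The recorded answer is Yes or No to a relationship with the Merck product.
- Likely cause: the investigator considers "another etiology such as underlying disease, other drug(s)/vaccine(s" and similar factors as alternative explanations.
- Dechallenge: "Was the Merck product discontinued or dose/exposure/frequency reduced". One ground for marking this item not applicable is that "the AE resolved/improved despite continuation" of the Merck product occurred. Rechallenge is also framed around re-exposure to the Merck product.
- Guidance on the answer: "not all criteria must be present to be indicative of a Merck product relationship"; one ground for No is that "there is another obvious cause of the AE".

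Section 8.2 defines a Merck product as one "manufactured by, licensed by, provided by or distributed by Merck for human use". Section 8.2.1 uses the term for pembrolizumab when it defines overdose, and Table 7 (Section 11.1) lists only pembrolizumab as supplied by Merck. Table 6 never names ipilimumab. Some of its labels and guidance lines do use wider terms, referring to the test drug and to the profile of the trial treatment.

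**The concern.** The regimen has two drugs, and the safety objective in Section 3.2 is about giving them together. If the form of evaluation asks about only one of them, the event-level record of causality and of drug stoppage is incomplete for the other. Section 10.1 specifies no adverse event summary, so no analysis rule would make good what the data fields leave out. Summaries of treatment-related events, or of events leading to discontinuation, could understate the toxicity of the combination if they were drawn from the Table 6 items alone.

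**Working it through.** No arithmetic on event rates applies. The check is to set the sections side by side and follow the wording through.

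**Which drug each section asks about**

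| Section | Subject of causality or action |
|---|---|
| 3.2, secondary safety objective | the combination |
| 5.2.1.2, discussion of Grade 3-5 events | study agent(s) |
| 5.6.1, supportive care | pembrolizumab and/or ipilimumab |
| 8.1.1.6, adverse event monitoring | trial treatment, for action taken |
| 8.2.3.3, adverse reaction | the study agent |
| 8.2.4, questions in Table 6 | the Merck product |

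Section 8.1.1.6 has the broader wording, but for detail it sends the reader to Section 7.2. Section 8.1.3.1 gives the title of that section as the one on assessing and recording adverse events, which in the present numbering is 8.2. The broad rule therefore leads to the part of the protocol that holds Table 6.

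**Step 1: action taken.** Table 3 has ten toxicity categories: diarrhea/colitis; AST, ALT or bilirubin; type 1 diabetes/hyperglycemia; hypophysitis; hyperthyroidism; hypothyroidism; infusion reaction; pneumonitis; renal failure/nephritis; all other. Two of the ten state a permanent stop of ipilimumab without the same for pembrolizumab: Grade 3 diarrhea/colitis, and type 1 diabetes/hyperglycemia. Section 5.2.1.2 also lets pembrolizumab continue, with the Principal Investigator's approval, after ipilimumab is stopped for toxicity. In each case the literal answer to the Table 6 question is No. That answer is true of pembrolizumab, but it does not show that ipilimumab was stopped.

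**Step 2: causality.** Suppose the investigator attributes an event solely to ipilimumab. Under Section 8.2.3.3 it is an adverse reaction. Under Table 6, ipilimumab can count among the other drugs and as another obvious cause, both of which support No. The same event can then be a reaction in one section and unrelated in another.

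**Step 3: dechallenge.** The item covers reduced exposure as well as discontinuation. In both Table 3 categories above pembrolizumab is also held. For diabetes/hyperglycemia the table says so directly. For diarrhea/colitis the hold-grade cell is blank in the text available, but Grade 4 has its own row and the Grade 3 wording stands in the row with a restart condition. A hold can reasonably be read as reduced exposure, so the item can apply. The gap arises only where ipilimumab is stopped with no pembrolizumab hold and the event then improves: the item becomes not applicable, and the response to stopping ipilimumab is not captured there.

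**Step 4: serious events.** Section 8.2.3.1 requires serious events inside the window to be reported whatever their relationship. Outside the window the trigger is relationship to the Merck product. Section 8.2.5 covers unexpected adverse reactions, so what remains is a late, expected serious event attributed solely to ipilimumab, which is a very narrow case.

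**The case against.** The strongest reply is that this is loose template language, not a deliberate restriction. Table 6 itself uses test drug and trial treatment in places, its criteria are guidance, and the threshold for Yes is only a reasonable possibility. Both drugs start together, so an event attributed to ipilimumab alone would be hard to establish. Section 5.2.1.2 requires the reason for discontinuation to be recorded and sends related Grade 3-5 events to the Principal Investigator; Section 8.1.1.6 asks for action taken on trial treatment. No planned analysis in Section 10.1 is shown to change.

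Much of this stands. It makes miscoding of causality a possibility and not a certainty, and it means an ipilimumab stop should be recorded somewhere. It does not remove the conflict. The questions and answers in Table 6 all say Merck product, the table states that the relationship assessment goes onto the case report forms or worksheets, and neither a recorded reason for stopping nor a discussion with the Principal Investigator supplies a causality or dechallenge entry for the event.

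Three stronger readings are tempting, and the documents do not support them.

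- *The event would be entered as having led to no action.* Table 6 has no such entry. It asks only whether the Merck product was discontinued.
- *Dechallenge information is lost in the two Table 3 categories.* Pembrolizumab is held in both, so the item can apply.
- *A number of missed ipilimumab stops can be projected from the phase I combination study in Section 4.2.2.* That section prints ipilimumab-only discontinuation as 5 patients (18.2%). With the 22 patients implied by 3/22 = 13.6%, 5/22 = 22.7% and 4/22 = 18.2%, so the count and the percentage disagree. The events were of any attribution, and nothing shows that the rate carries over to this trial. The figure shows only that such stops occur.

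**Conclusion.** The concern holds as a conflict of wording with a limited consequence. Followed as written, the Table 6 items do not show a permanent stop of ipilimumab alone, and they allow an event attributed solely to ipilimumab to be recorded as unrelated. In terms of rules, 2 of the 10 toxicity categories in Table 3 foresee such a stop. In terms of events, the size cannot be estimated: the documents give no rate of events attributed solely to ipilimumab and do not include the case report form.

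All-cause adverse events, grades, in-window serious events and the primary endpoint are unaffected. A reader might infer that safety reporting as a whole is unreliable; the documents do not support that.

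The conclusion rests on two assumptions. First, Merck product means pembrolizumab. This is inferred from Sections 8.2, 8.2.1 and 11.1, since the documents do not say who supplies ipilimumab. Even if ipilimumab were included, one question could not show which drug was stopped. Second, the case report form follows Table 6. If it already has fields for both drugs, only the protocol wording needs correction.

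**What to change.** Reconcile Table 6 with Sections 5.2.1.2, 5.6.1, 8.1.1.6 and 8.2.3.3:

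1. Word the action-taken, causality, dechallenge and rechallenge items for trial treatment (pembrolizumab and/or ipilimumab).
2. Record which drug was stopped.
3. State that an event counts as treatment-related if it is related to either drug or to both.
4. Align the sentence on out-of-window serious events in Section 8.2.3.1 in the same way.

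Separate causality fields for each drug are optional; attribution to one drug is hard while both are given together, and the common wording already removes the conflict. None of this alters a dosing or stopping rule.

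The cost is minor wording changes and one or two data fields. Rates of treatment-related events may look slightly less favourable.
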